4.2.4 Dexamethasone blood draw

Blood samples for dexamethasone measurement will be drawn as follows:

- Designated subset of subjects
 - Approximately 30-60 minutes after sensor insertion is complete
 - 2 additional samples, timing to be specified, within approximately 4 hours of the sensor insertion.
- All remaining subjects
 - One sample drawn based on analysis of dexamethasone from subset group.

All samples will be collected and processed as described in the operations manual.

4.2.5 Device disbursement

Subjects will be assigned the following devices:

- Senseonics Continuous Glucose Monitoring (CGM) Systems consisting of
 - One Gen 1 Transmitter and accessories (charger, adhesive patches)- PRIMARY- Displays glucose
 - One Gen 2 Transmitter and accessories (charger, adhesive patches)- SECONDARY - Does not display glucose (subjects inserted with one sensor only will not use this system)
 - Handheld Device (1 per Subject) running the Mobile Medical Application (MMA)
 - Eversense CGM User Guides

- A widely-used, commercially available FDA-approved self-monitoring blood glucose (SMBG) meter and associated supplies-
 - BG meter strips
 - Lancets
 - control solution
 - Instructions for Use

4.2.6 Subject training

Subjects will be issued one or two transmitters as applicable. Gen 1 and Gen 2 transmitters will be visually distinguishable from each other to ensure matching to the correct limb.

Subjects participating in the subset for additional dexamethasone testing will only be issued the Gen 1 transmitter. Each transmitter is linked to a specific sensor as described in the Eversense CGM User Guide. Subjects will be issued a hand held device which will be used for entering calibration information into the Gen 1 transmitter only. The Gen 2 transmitter worn on the opposite arm will have the ability to collect and log data only and will not calculate and store glucose information.

The subject will be given instructions on how to contact study staff for 24 hours per day to report any study- related problems. The subject will be instructed to contact the study staff for prolonged hyperglycemia, severe hypoglycemia, or if he/she experiences nausea, vomiting, or abdominal pain within 48 hours after discharge. The subject will be instructed to contact the study staff for any problems related to the sensor sites, including fever, pain, redness, itching, discharge, warmth or swelling at the sensor insertion sites. If infection is experienced, standard medical practice and administration of antibiotics as required should be followed until resolution. Subjects will be further instructed to advise the investigator if new medications have been prescribed or started, or if any hospitalizations or significant medical changes have occurred.

The subject will be instructed on the proper use and quality control of the Subject SMBG Meter including the number and timing of fingersticks expected during each day (approximately 7 times per day (before meals, approximately 2 hours after meals, and at bedtime)).

The subject will be instructed on the proper use of the Transmitter and Mobile Medical Application (refer to the Eversense CGM User Guides). The transmitter will be worn over the sensor at all times (except while charging, bathing or during any other water activities) starting approximately 24 hours post insertion. Subjects will be prompted to calibrate the sensor using fingerstick measurements (a minimum of 2 each day, approximately 12 hours apart) using the Subject SMBG meter.

Training may continue at Visit 3, or as needed.

4.2.7 Discharge

Discharge will occur upon completion of confirmation of system operation and subject training. The site will document any adverse events that may have occurred during the visit.

When subjects leave the clinic after completing the sensor insertion/training visit, they will NOT bring the transmitters or study-supplied meter home with them. Transmitters and study-supplied meters will remain at the site overnight and issued to the subject for home use at visit 3. Subjects may take the HHD home with them overnight in order to pair with their home wifi, and to familiarize themselves with the MMA.

4.2.8 Estimated Total Blood Volume

The total amount of blood will not exceed 12 ml plus fingersticks taken during the visit.

4.2.9 Estimated Visit Duration

The total duration of the inpatient visit is approximately 2-6 hours.

4.3 Subset of subjects for dexamethasone analysis

A designated subset of a minimum of 6 and a maximum of 9 subjects across the study will return on days 3-6 for blood draws (~ 4 mL each) for dexamethasone analysis. These samples are in addition to the samples collected at visit 3 on days 1 and 2 and at visit 4 on days 7 and 8 (as described below).

Dexamethasone results from these subjects will be used to determine whether and when the remaining subjects will need to come in for an additional blood draw for dexamethasone measurement. This may occur within several hours of sensor insertion (at the end of Visit 2), or during the first 7 days post sensor insertion.

4.4 Sensor Accuracy (Sampling) Visit 3 – Day 1 (\pm 0 Days)

Approximate visit duration - 19 hours

Approximate sampling duration – 16 hours

Approximate visit timeline:

Approximate time	Activity	~Time relative to first IV sample
~16:00	Admission and First Calibration	T=0 -2:00
~16:30	Blood draw for dexamethasone	T=0 -1:30
~17:00	Fingerstick	T=0 -1:00
~17:15-17:45	Period for glucose stabilization	T=0 -0:45 - -0:15
~18:00	First IV blood sample drawn/ second calibration	T=0 0:00
~18:00 – 0:00	For qualifying subjects, hyperglycemia challenge to achieve hyperglycemia to goal glucose >350 mg/dL. 
 Sampling @ 5 min when glucose ≥ 325 mg/dL, with a target duration of 1 hour. Challenge may be stopped once 12 samples ≥325 mg/dL are collected. 	T=0 0:00 – +6:00
19:00	Fingerstick	T=0 0:00 - +1:00
~20:00	Third calibration	T=0 0:00 - +2:00
21:00	Fingerstick	T=0 0:00 - +3:00
~22:00	Fourth calibration	T=0 0:00 - +4:00
~23:00	Fingerstick	T=0 0:00 - +5:00
~0:00	Fingerstick	T=0 0:00 - +6:00
~0:00-07:00	Overnight period 
 Overnight period. Sampling q 15 min when glucose is > 75 mg/dL and < 325 mg/dL. Q 5 minutes when outside this range. 	T=0 +6:00 - +13:00
~07:00	CGM system calibration	T=0 +13:00

Approximate time	Activity	~Time relative to first IV sample
~07:00-10:00	
For qualifying subjects, hypoglycemia challenge to achieve hypoglycemia target <60 mg/dL.
 
 Sampling q 5 min when glucose ≤ 75mg/dL. Target 24 YSI values <75 mg/dL, including 6 YSI values <60 mg/dL at q 5 min before rescue. Subjects fed low glycemic morning meal and YSI data collection discontinued once challenge is concluded. Hourly fingersticks from 07:00 to 11:00. 	T=0 +13:00 - +16:00
~08:00	Fingerstick	T=0 +13:00 - +14:00
~09:00	Fingerstick	T=0 +13:00 - +15:00
~10:00	Fingerstick	T=0 +13:00 - +16:00
~10:00-11:00	Discharge preparation	T=0 +16:00 - +17:00
~10:30	Blood draw for dexamethasone	T=0 +16:30
~11:00	Discharge	T=0 +17:00

4.4.1 Device preparation

All Study devices will be time synchronized and checked for function as described in section 5.3.

4.4.2 Medications and Medical Supplies

Medications and medical supply status will be checked as described in Section 5.2.

4.4.3 Meals

Other than during glucose challenges, subjects will be allowed to eat, drink and continue his/her diabetes treatment regimen throughout the admission. Specific information regarding subject meals is described in Section 5.13.

4.4.4 Subject Instructions prior to admission

Prior to admission, subjects should take their medications and food as follows:

- Subjects participating in hyperglycemia challenge soon after admission should not take subcutaneous bolus insulin approximately 3 hours prior to the challenge. Subjects should take their normal dose and timing of basal insulin. If challenge subjects need to eat or take insulin for safety reasons, they should inform study staff of this information on arrival to the clinic.
- If subjects blood glucose is <150 mg/dL they should be instructed to eat a snack prior to coming to the clinic, and be given specific instructions how to modify basal infusion until they arrive at the study site. Subjects may receive guidance from study staff trained in diabetes treatment regarding insulin and carbohydrate intake prior to the visit.

4.4.5 Subject Admission

The subject will arrive at the clinic during the day, no later than approximately 16:00 and the following tests will be performed to confirm eligibility for participation in visit 3:

- Hematocrit will be assessed using local lab or Point of Care testing device. Subject must be within reference range to participate in accuracy (sampling) visit.
- Female subjects of childbearing capacity will perform a urine pregnancy test. If positive, the subject will discontinue study participation. Subject withdrawal will be documented.
- The study team will confirm the absence of a febrile or vomiting illness within 24 hours of the admission.
- The study team will confirm that the subject brought his/her personal insulin and insulin pump or injection supplies (as applicable) and required medications. The subject will continue to use his/her diabetes treatment regimen throughout the admission. The subject will be rescheduled if he/she did not bring his/her required medications or appropriate medications are not available at the clinic.
- Clinical staff to confirm that the transmitters and hand held device are in communication and functioning.
- If all admission readiness criteria are not met, the subject will be rescheduled. If all of the admission readiness conditions are met, the subject will be admitted to the Clinical Research Unit. NOTE: If rescheduling is required, Clinicians should make every effort to reschedule the visit within 1-3 days from the originally scheduled visit. Rescheduling of Visit 3 for safety reasons will not be considered a protocol deviation.

4.4.6 Adverse events

Upon admission subject will be asked about any adverse events or changes to medications since the last study visit. Adverse events will be documented on the appropriate eCRF.

4.4.7 Dexamethasone blood draw

Blood sample will be drawn at the beginning of the visit, and again at the end of the visit prior to discharge for dexamethasone measurement. All samples will be collected and processed as described in the operations manual.

4.4.8 Ketone testing

On arrival to the clinic, subject blood ketones should be evaluated from capillary blood using the ketone meter. If ketones are ≥ 0.6 mmol/L, ketone testing should be repeated as described in Section 5.8 and subjects should be treated for ketones following ketone treatment guidelines Section 7.1.5.

4.4.9 SMBG testing

During in-clinic days, subjects should continue testing blood sugar using the study-supplied Subject SMBG Meter following the study visit timeline (hourly, except during overnight period).

4.4.10 IV placement

Intravenous (IV) access appropriate for blood drawing and potential intravenous rescue (such as dextrose or glucagon) will be established following the IV placement guidelines (Section 5.9)

4.4.11 Blood sampling for glucose measurement

Once IV access has been established, blood will be sampled for bedside reference glucose every 5-15 minutes per the Blood Sampling guidelines (Section 5.9).

4.4.12 Hyperglycemia Challenge

For qualifying subjects, a hyperglycemia challenge will be conducted to achieve a glucose goal of >350 mg/dL. Sampling interval will be q 5 min when glucose ≥ 325 mg/dL for a target of 1 hour before rescue. For those subjects not following a basal/bolus routine on MDI or CSII, glucose control will be free range. Details regarding conduct of the hyperglycemia challenge can be found in Section 5.12.

4.4.13 Hypoglycemia Challenge

For qualifying subjects, a hypoglycemia challenge will be conducted to achieve a glucose goal of ≤ 60 mg/dL. Sampling interval will be q 5 min when glucose ≤ 75 mg/dL for a target of 2 hours before rescue. For those subjects not following a basal/bolus routine on MDI or CSII, glucose control will be free range. Details regarding conduct of the hypoglycemia challenge can be found in Section 5.12.

4.4.14 Observation subjects

Subjects with gastroparesis or those subjects unable to participate in glucose challenges will participate in the sampling sessions using free range glucose control.

4.4.15 Discharge instructions

The discharge procedure will occur upon completion of ~approximately 16 hours of IV blood sampling. Discharge instructions are detailed in Section 5.14.

4.4.16 Estimated Total Blood Volume

Approximately 89 blood samples will be obtained throughout the course of the visit in addition to the blood sample required for dexamethasone analysis and fingersticks taken.

The maximum estimated amount of blood estimated for the visit is 97 ml.

4.4.17 Estimated Visit Duration

The total duration of the inpatient visit is approximately 19 hours. The study time may be extended for glucose stabilization prior to discharge.

4.5 Sensor Accuracy (Sampling) Overnight Visits

Visit 4 – Day 7 Accuracy (Sampling) Visit (± 1 Day)

Visit 5 – Day 14 Accuracy (Sampling) Visit (± 1 Day)

Approximate visit duration – 18 hours

Approximate sampling duration – 16 hours

Approximate visit timeline:

Approximate time	Activity	Time relative to first IV sample
~17:00	Admission	T=0 -1:00
~17:15-17:45	Period for glucose stabilization and CGM calibration	T=0 -0:45 - -0:15
~17:30	Blood draw for dexamethasone, prior to YSI sampling	
~18:00	First IV blood sample drawn	T=0 0:00
~18:00 – 0:00	
For qualifying subjects, hyperglycemia challenge to achieve hyperglycemia to goal glucose >350 mg/dL.Sampling @ 5 min when glucose \geq 325 mg/dL, with a target duration of 1 hour.
Challenge may be stopped once 12 samples \geq325 mg/dL are collected.	T=0 0:00 – +6:00
~19:00	Fingerstick blood glucose	T=0 +1:00
~20:00	Fingerstick blood glucose	T=0 +2:00
~21:00	Fingerstick blood glucose	T=0 +3:00

Approximate time	Activity	Time relative to first IV sample
~22:00	Fingerstick blood glucose	T=0 +4:00
~23:00	Fingerstick blood glucose	T=0 +5:00
~0:00	Fingerstick blood glucose	T=0 +6:00
~0:00-07:00	
 Overnight period. Sampling q 15 min when glucose is > 75 mg/dL and < 325 mg/dL. Q 5 minutes when outside this range. 	T=0 +6:00 - +13:00
~07:00	Fingerstick blood glucose and sensor calibration	T=0 +13:00
~07:00-10:00	
For qualifying subjects, hypoglycemia challenge to achieve hypoglycemia target <60 mg/dL.
 
 Sampling q 5 min when glucose ≤ 75 mg/dL. Target 24 YSI values <75 mg/dL including 6 YSI values <60 mg/dL at q 5 min before rescue. 
Subjects fed low glycemic morning meal and YSI data collection discontinued once challenge is concluded.
	T=0 +13:00 - +16:00
~08:00	Fingerstick blood glucose	T=0 +14:00
~09:00	Fingerstick blood glucose	T=0 +15:00
~10:00	Fingerstick blood glucose	T=0 +16:00
~10:00-11:00	discharge preparation	T=0 +16:00 - +17:00
~10:30	Blood draw for dexamethasone after YSI sampling complete.	T=0 +16:30
~11:00	Discharge	T=0 +17:00

The following procedures/instructions will be followed for accuracy (sampling) visits at Visits 4 and 5:

4.5.1 Pre-visit phone call

One to two days prior to the Accuracy (Sampling) Visit, site personnel will contact the subject to ensure the subject is in compliance with study device wear. Subjects will also be advised if they are scheduled for a glucose challenge and will be given appropriate instructions regarding pre-visit medications and meals.

4.5.2 Device preparation

All Study devices will be time synchronized and checked for function as described in section 5.3

4.5.3 Medications and Medical Supplies

Medications and medical supply status will be checked as described in Section 5.2.

4.5.4 Meals

Specific information regarding subject meals is described in Section 5.13. Food and drink will be controlled as required.

4.5.5 Subject Instructions prior to admission

Prior to admission, subjects should take medications and meals as usual as follows:

- Subjects participating in hyperglycemia challenge soon after admission should not take subcutaneous bolus insulin approximately 3 hours prior to the challenge. Subjects should take their normal dose and timing of basal insulin. If challenge subjects need to eat or take insulin for safety reasons, they should inform study staff of this information on arrival to the clinic.
- If subjects blood glucose is <150 mg/dL they should be instructed to eat a snack prior to coming to the clinic, and be given specific instructions how to modify basal infusion until they arrive at the study site.

4.5.6 Subject Admission

The subject will arrive at the clinic during the day, no later than approximately 17:00 and the following tests will be performed to confirm eligibility for participation in visits 4 and 5:

- Hematocrit will be assessed using local lab or Point of Care testing device. Subject must be within reference range to participate in accuracy (sampling) visit.
- Female subjects of childbearing capacity will perform a urine pregnancy test. If positive, the subject will discontinue study participation. Subject withdrawal will be documented. The study team will confirm the absence of a febrile or vomiting illness within 24 hours of the admission.
- The study team will confirm that the subject brought his/her personal insulin and insulin pump or injection supplies (as applicable) and regular medications. The subject will continue to use his/her diabetes treatment regimen throughout the admission. The subject will be rescheduled if he/she did not bring his/her regular medications or appropriate medications are not available at the clinic.
- Clinical staff to confirm that the subject is wearing the transmitters and that the transmitters and hand held device are in communication and functioning.

- The subject will be rescheduled if he/she did not bring his/her Transmitters and cannot make them available during the visit.
- If all admission readiness criteria are not met, the subject will be rescheduled. If all of the admission readiness conditions are met, the subject will be admitted to the Clinical Research Unit.

4.5.7 Adverse events

Upon admission subject will be asked about any adverse events or changes in medication since the last study visit. The sensor insertion site will be examined. Adverse events including those associated with the insertion site will be documented on the appropriate eCRF.

4.5.8 Dexamethasone blood draw

Blood sample will be drawn at the beginning of the visit and prior to discharge for Dexamethasone measurement. All samples will be collected and processed as described in the operations manual.

4.5.9 Ketone testing

On arrival to the clinic, subject blood ketones should be evaluated from capillary blood using the ketone meter. If ketones are ≥ 0.6 mmol/L, ketone testing should be repeated as described in Section 5.8 and subjects should be treated for ketones following ketone treatment guidelines Section 7.1.5.

4.5.10 SMBG testing

During in-clinic days, subjects should continue testing blood sugar using the study-supplied Subject SMBG Meter following the visit schedule (hourly except during overnight period).

4.5.11 IV placement

Intravenous access appropriate for blood drawing and potential intravenous dextrose or other medically necessary and appropriate rescue will be established following the IV placement guidelines (Section 5.9).

4.5.12 Blood sampling for glucose measurement

Once IV access has been established, blood will be sampled for bedside reference glucose every 5-15 minutes per the Blood Sampling guidelines (Section 5.9).

4.5.13 Calibration (Visits 4 & 5)

Subjects/clinicians will calibrate the system during the time period for glucose stabilization and will calibrate again approximately 12 hours later. The morning calibration reminder, adjusted through use of the HHD and mobile medical application will be set to approximately 12 hours after the evening calibration entry.

4.5.14 Glucose Challenges

Qualifying subjects will participate in hyperglycemia and hypoglycemia challenges during the times indicated in the visit timeline table. The intention of the hypoglycemia and hyperglycemia challenge is to safely manipulate the subject's blood glucose levels so that sensor performance can be evaluated over a wider range than might otherwise be observed. Details regarding the glucose challenges can be found in Section 5.12.

4.5.15 Observation subjects

Subjects with gastroparesis or those subjects unable to participate in glucose challenges will participate in the sampling sessions using free range glucose control.

4.5.16 Sleep Assessment

Designated subjects will be inserted with two sensors, one in each upper arm. Each subject will spend two overnights in the clinic where they will be instructed to sleep on one side for situations in which compression of the sensor site may occur during sleep. "Sensor drop-out," if a phenomenon of the Senseonics CGM System, will be identified during these periods. Sleep position will not be documented.

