I agree to conduct this clinical investigation in accordance with the design and specific provisions of this protocol and all applicable regulatory requirements. Modifications to the clinical investigation are acceptable only with a mutually agreed upon protocol amendment as approved by the sponsor, regulatory bodies and Institutional Review Board/ Ethics Committee. I agree to await Institutional Review Board/ Ethics Committee approval of the protocol, informed consent, and sponsor approval before initiating the study, and to obtain consent from subjects prior to their enrollment in the study. I agree to collect and record data as required by the protocol and case report forms, and to maintain study documents for the period of time required.

Confidential

This document contains confidential information belonging to Senseonics, Inc. Except as may be otherwise agreed to in writing, by accepting or reviewing these materials, I agree to hold such information in confidence and not to disclose it to others (except where required by applicable law), nor use it for unauthorized purposes.

Investigator's signature

Date of signature

SYNOPSIS

Title of Protocol	PRECISION Study: A Prospective , Multicenter Evaluation of Precision , Compression , Accuracy and Updated Algorithm of a Novel Continuous Implanted Glucose Sensor
Sponsor	Senseonics, Inc.
Investigational Device	Senseonics Continuous Glucose Monitoring (CGM) System (the "System")
Reference Instrument	Reference Glucose Analyzer (bedside, YSI 2300 STAT PLUS® Glucose and Lactate Analyzer, Yellow Springs Instruments, Yellow Springs, OH, USA).
Calibration Standard	FDA-cleared Blood Glucose Meter (Subject SMBG Meter)
Study Purpose	The purpose of this clinical investigation is to evaluate the precision and accuracy of the Senseonics Continuous Glucose Monitoring System (Senseonics CGM System) measurements when compared with reference standard measurements. Compression of the sensor site and use of a new algorithm will also be evaluated. The investigation will also evaluate safety of the Senseonics CGM System usage.

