3.3 Study Design

3.3.1 Overview

This is a non-randomized, prospective, single-arm, multi-center study, whereby approximately 44 subjects will be enrolled and 36 subjects will be inserted in the United States at up to 4 sites. The investigation will include both clinic visits and home use of the Senseonics CGM System. The subjects will have one or two Sensors inserted by trained Investigators. The Sensors will be inserted in the upper arms of the subjects. The accuracy of the Senseonics CGM System will be evaluated during clinic visits comparing Sensor glucose values and plasma glucose values measured on a bedside glucose analyzer. For qualifying subjects, during the clinic visits, there will be planned hyperglycemia and hypoglycemia challenges, as described in Section 5.12. Effects of compression/sensor dropout will be evaluated during the designated overnight periods.

In this study, including the clinic and home settings, all diabetes care decisions will be based on SMBG blood glucose values and clinical standard of care, rather than Senseonics CGM System results.

This study will not be randomized. Subjects will be selected consecutively (i.e., selecting every subject in the order they present at the site) among those who meet the inclusion/exclusion criteria.

The Subject visit schedule includes 9 visits over a period of approximately 4.5 months (inclusive of visit windows from screening visit through follow-up visit).

A subset of a minimum of 6 and a maximum of 9 subjects will have blood samples drawn daily for the first 7 days of sensor wear for additional dexamethasone screening and to determine blood draw time points during the first week of sensor wear for the remaining subjects. These subjects will only have one sensor inserted in the left arm, which will be linked to the Gen 1 transmitter. Remaining subjects will have 2 sensors inserted, one in each arm, with the left sensor linked to a Gen 1 transmitter, and the right sensor linked to the Gen 2 transmitter. These subjects may be required to make additional visits for dexamethasone screening between visits 3 and 4.

The study is anticipated to take approximately 6 months, including the enrollment period.

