11.3.2.8 Effect of compression on sensor performance during sleep challenges

For the sleep assessment periods during visits 4 & 5, compression may occur to the sensor site when the subject is sleeping at night. The system's difference and agreement with reference and between system precision will be compared between the night time and the day time (Tables 10A and 10B in APPENDIX 1).

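### The compression assessment records neither the instructed sleep side nor the actual position, and its night-versus-day comparison cannot separate moderate compression from other night-day differences

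*Protocol*

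**What the plan says.** - **Purpose.** Compression is in the study title. The Protocol synopsis (Study Purpose) says "Compression of the sensor site and use of a new algorithm will also be evaluated". Protocol 3.3.1 says "Effects of compression/sensor dropout will be evaluated during the designated overnight periods", and SAP section 3 repeats it.
- **Exposure.** Protocol 4.5.16, on two-sensor subjects: "Each subject will spend two overnights in the clinic where they will be instructed to sleep on one side". The same paragraph ends "Sleep position will not be documented". Neither document says which side, how it is chosen, whether it changes between Visits 4 and 5, or that it is written down. The schedules of events (Protocol section 4, SAP 5.1) only mark the assessment at those visits.
- **Hardware.** In two-sensor subjects the left sensor has the Gen 1 transmitter and the right sensor the Gen 2 (Protocol 3.3.1). Only the primary system is calibrated in use; the secondary only logs data (Protocol 1.1.2, 4.2.6).
- **Analysis.** Protocol 11.3.2.8 and SAP 6.10.1.7 plan one comparison, for accuracy and agreement against the reference and for the two sensors against each other: "between system precision will be compared between the night time and the day time". Tables 10A and 10B report it. SAP Appendix 2, Tables 2.10 and 2.11, repeat it by transmitter and firmware configuration. Night and day are not defined.
- **Timeline, Visits 4 and 5 (Protocol 4.5).** The overnight period is about 00:00-07:00, with "Sampling q 15 min when glucose is > 75 mg/dL and < 325 mg/dL" and 5-minute sampling outside that range. Challenge windows run from about 18:00 to 00:00 and from 07:00 to 10:00. Calibration is at about 17:15-17:45, then at 07:00 ("Fingerstick blood glucose and sensor calibration"). Protocol 4.5.13 instead says that subjects or clinicians "will calibrate again approximately 12 hours later".
- **Drop-out.** Protocol 4.5.16 intends to identify sensor drop-out in these periods. It gives no criterion.

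**The concern.** The design sets up a strong comparison: two sensors in the same person, at the same time and at the same blood glucose, with one arm more likely to be loaded. Using it requires knowing which arm that was meant to be, and the plan does not keep that information. What remains is night against day, and the two periods differ in more than compression. At stake is whether the study can answer a question that it names in its title and purpose.

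**Working it through.** **1. Subjects and night data.** Protocol 11.1.4 assumes 66 sensors. With 36 subjects inserted and 6 to 9 given one sensor, 6 + 2×30 = 66 and 9 + 2×27 = 63. The 66 is reproduced, and there are 27 to 30 two-sensor subjects. A full night at 15-minute spacing gives 7×4 = 28 YSI times. Over two nights that is 27×2×28 = 1,512 to 30×2×28 = 1,680. This is a minimum for full nights, because sampling moves to every 5 minutes outside the range. Data volume is not the problem.

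**2. Time since primary calibration.** Assumptions: night is 00:00-07:00, day is the other 9 sampling hours (18:00-00:00 and 07:00-10:00), and evening calibration is at 17:30.

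- Recalibration at 07:00 (4.5 timeline): night ages run from 6.5 to 13.5 h, mean 10.0 h. Day: (6×3.5 + 3×1.5)/9 = 2.8 h.
- Recalibration at 05:30 (4.5.13, 12 h later): night (5.5×9.25 + 1.5×0.75)/7 = 7.4 h. Day: (6×3.5 + 3×3.0)/9 = 3.3 h.
- Moving the evening calibration within 17:15-17:45 gives 9.75-10.25 against 2.7-3.0 h, and 7.25-7.6 against 3.1-3.6 h.

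**3. Can the calibration-stability table (SAP Table 25) separate the two?** Hours falling in each bin at Visits 4 and 5:

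| Time from calibration | Night / day, recalibration 07:00 | Night / day, recalibration 05:30 |
|---|---|---|
| 0-4 h | 0 / 6.5 | 1.5 / 6 |
| 4-8 h | 1.5 / 2.5 | 1.5 / 3 |
| 8-12 h | 4 / 0 | 4 / 0 |
| over 12 h (not in table) | 1.5 / 0 | 0 / 0 |

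On either timeline the 8-12 h bin is all night, so at these visits it cannot distinguish calibration age from night. Accuracy by glucose range, rate of change and time since calibration is planned, also by visit day (SAP 6.10), but not crossed with night and day.

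**4. What Table 10A estimates.** Let c be the MARD points added while a sensor is loaded, f the share of the night for which one of the two sensors is loaded, and d the night-minus-day difference from everything else. Pooled over both sensors, night minus day = d + c·f/2. With assumed values and f = 1:

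- c = 0, d = +3 gives +3; c = 6, d = 0 also gives +3.
- c = 0, d = 0 gives 0; c = 6, d = -3 also gives 0.

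**5. Reading Tables 10A and 10B together.** Simulation of 30 two-sensor subjects with 56 night and 122 day readings per sensor and the loaded side random across subjects. All error sizes and effects are assumed. Results are night minus day, in points:

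| Scenario | MARD | PARD |
|---|---|---|
| No compression, noisier night (error SD 0.13 v 0.11) | +1.5 | +2.1 |
| 20% low bias, f = 0.25, equal noise | +1.3 | +2.7 |
| 20% low bias, f = 0.25, noisier day (0.14 v 0.11) | -0.9 | -0.5 |
| 40% low bias, f = 0.5, equal noise | +7.4 | +18.0 |

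The first two rows are nearly the same pattern, and in the third the effect is hidden. The fourth would be noticed.

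**6. The split by transmitter.** With a 20% bias and f = 0.5, left and right move by +2.55 and +2.59. If the unrecorded side varies across subjects, Table 2.10 shows no contrast. If everyone lay on the same side, loading would be tied to one transmitter generation.

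**The case against.** The strongest reply is that the plan offers more than one bare night-day figure, and much of that stands.

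- Tables 2.10 and 2.11 cross night and day with configuration, hence with arm. A reader might infer that the comparison is not crossed with anything; that is not so. But arm is inseparable from hardware, and the comparison is not crossed with instructed side, glucose range, rate of change or calibration age.
- Table 10B compares a subject's two sensors at the same time. A reader might infer that the plan can neither show nor exclude compression of any size; that goes too far, since a gross one-sided effect would raise PARD. PARD is unsigned, however, and does not say which sensor was loaded.
- The Day 30, 60 and 90 versions of Table 25 provide a partial control. With calibration at about 07:30, the 8-12 h bin is about 15:30-19:30, daytime and mostly in the free-range period of 16:00-19:30. Sensor age differs from Days 7 and 14, so the control is not clean.
- Challenge windows are not the same as challenge-level glucose. In Protocol 11.1.4, the 40-60 and 350-400 mg/dL bins hold 166 + 65 = 231 of 4,632 pairs per 16-hour session (5%). Adding all of 61-80 and 301-350, which overcounts, gives 804 (17%).
- Night drop-out is not wholly invisible: Tables 10A and 10B give pair counts by night. What is missing is a criterion and an expected count.
- The Study Operations Manual is not available and might assign a side. Section 4.5.16 does not refer to it.
- The measure is exploratory and descriptive, and the absence of position records is openly stated.

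**Conclusion.** The point holds in a limited form. A moderate night-day difference at Visits 4 and 5 cannot be attributed to compression, and a small one does not exclude it. The gap in mean time since primary calibration is about 7 h on the visit timeline (10.0 - 2.8 = 7.2) and about 4 h with recalibration 12 hours later (7.4 - 3.3 = 4.1). These figures rest on the assumed 00:00-07:00 night and apply to the primary system only, because the secondary system is not calibrated in use. The simulated values only illustrate the ambiguity; they do not predict results.

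A reader might infer that the effectiveness result is compromised. The documents do not support that: MARD does not depend on this comparison, and no hypothesis is tested. The change is worth making because the purpose is named and the missing item costs almost nothing to record.

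**What to change.** 1. Record the instructed side on the CRF at Visits 4 and 5. Alternate it between the visits and counterbalance the starting side across subjects, so that side is not tied to Gen 1 or Gen 2 within a visit.
2. Record each sensor's arm and transmitter, because Protocol 5.10 can move the Gen 1 transmitter to the other arm.
3. Define night and day by clock time.
4. Make the main compression description the within-subject, within-night contrast of instructed-side against other-side sensor, using signed relative difference, absolute relative difference and agreement. Keep night versus day as secondary.
5. Define a missing reading for each system. Report missing logged readings per sensor-night by side against the expected count: 7×12 = 84, if Gen 2 logs at the same 5-minute interval.

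The cost is one CRF field per overnight visit plus the arm and transmitter record, a line of site instruction, one re-specified table and the definitions. No extra samples or staff are needed.

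There are two downsides. Adherence to the instructed side stays unverified. If a share p of the night is spent on it, the contrast estimates between (2p-1)c (rest of the night on the other side) and p·c (rest unloaded): 0.8c to 0.9c at p = 0.9, 0.4c to 0.7c at p = 0.7, and 0 to 0.5c at p = 0.5. A null result is therefore informative only if adherence was good. The IV line in an arm or hand (Protocol 5.9.1) may also limit which side a subject can use.
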